### 8.2.2 Reporting Serious Adverse Events

Any SAE, including death, due to any cause that occurs during this investigation, whether or not related to the administration of study drug, must be reported to the Sponsor immediately (not to exceed 24 hours) by telephone or facsimile. The reaction must be completely described on the CRF and SAE report form.

### 9 ASSESSMENT OF ANTI-TUMOR ACTIVITY IN SOLID TUMORS

The following definitions and criteria (from Response Evaluation Criteria in Solid Tumors [RECIST 1.1, Eisenhauer et al. 2009] ) should be used for the baseline evaluations of existing disease, and for the ongoing evaluation of tumor responses.

Measurable disease - the presence of at least one measurable lesion.

Measurable lesions - lesions that can be accurately measured in at least one dimension with longest diameter  $\ge 10$  mm using conventional techniques or  $\ge 10$  mm with spiral CT scan. Malignant lymph nodes must be  $\ge 15$  mm in the shortest diameter.

Non-measurable lesions - all other lesions, including small lesions (longest diameter <10 mm with conventional techniques, <10 mm with spiral CT scan or ≥10 mm to <15 mm in short axis), i.e., bone lesions, ascites, pleural/pericardial effusion, cystic lesions and also abdominal masses that are not confirmed and followed by imaging techniques.

- All measurements should be taken and recorded in metric notation, using a ruler or calipers.
- The same method of assessment and the same technique should be used to characterize each identified and reported lesion at baseline and during follow-up.
- Lesions will only be considered measurable when they are superficial (e.g., skin nodules and palpable lymph nodes). For the case of skin lesions, documentation by color photography, and a measurement with a ruler to estimate the size of the lesion, is recommended.

### 9.1 Methods of Measurement

- CT and MRI are the best currently available and reproducible methods to measure target lesions selected for response assessment. Conventional CT and MRI should be performed with cuts of 10 mm or less in slice thickness contiguously. Spiral CT should be performed using a 5 mm contiguous reconstruction algorithm.
- All imaging methods should be performed according to institutional standards with each patient having consistency of methods beginning from baseline through the course of the study.

### 9.2 Baseline Documentation of "Target" and "Non-Target" Lesions

- All measurable lesions up to a maximum of five lesions total with a maximum of 2
  lesions per organ, representative of all involved organs should be identified as *target lesions* and recorded and measured at baseline.
- Target lesions should be selected on the basis of their size (lesions with the longest diameter) and their suitability for accurate repeated measurements (either by imaging techniques or clinical assessments).
- A sum of the longest diameter (LD) for *all target lesions* will be calculated and reported as the baseline sum LD. The baseline sum LD will be used as the reference by which to characterize the objective tumor response.
- All other lesions (or sites of disease) should be identified as *non-target lesions* and should also be recorded at baseline. Measurements of these lesions are not required, but the presence or absence of each should be noted throughout follow-up.

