### 9.3 Response Criteria

	Evaluation of target lesions
Complete Response (CR):	Disappearance of all target lesions
	Any pathological lymph nodes must have reduction in short
	axis of <10mm
Partial Response (PR):	At least a 30% decrease in the sum of the LD of target
	lesions, taking as reference the baseline sum LD
Progressive Disease (PD):	At least a 20% increase in the sum of the LD of target
	lesions, taking as reference the smallest sum LD recorded
	since the treatment started. In addition to the increase of
	20%, the sum must also demonstrate an absolute increase of
	at least 5mm. The appearance of one or more new lesions is
	also considered progression
Stable Disease (SD):	Neither sufficient shrinkage to qualify for PR nor sufficient
	increase to qualify for PD, taking as reference the smallest
	sum LD since the treatment started
	Evaluation of non-target lesions
Complete Response (CR):	Disappearance of all non-target lesions and normalization of

	Evaluation of non-target lesions
Complete Response (CR):	Disappearance of all non-target lesions and normalization of
	tumor marker level. All lymph nodes must be non-
	pathological in size (<10mm short axis)
Stable Disease (SD):	Persistence of one or more non-target lesion(s) and/or
	maintenance of tumor marker level above normal limits
Progressive Disease (PD):	Appearance of one or more new lesions and/or unequivocal
	progression of existing non-target lesions

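### Lymph nodes qualify and reach CR on short axis but are scored for PR, SD and PD on longest diameter, so a node's category can depend on the axis, in either direction

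*Protocol*

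**What the plan says.** **Nodes judged on short axis.** Protocol Section 9 requires a malignant node to reach 15 "mm in the shortest diameter" to be measurable. It lists as non-measurable those lesions that are "<10 mm with spiral CT scan or ≥10 mm to <15 mm in short axis". For target-lesion CR, Protocol 9.3 begins its nodal line "Any pathological lymph nodes must have reduction in short" axis and gives 10 mm as the limit. SAP Appendix 1.1 repeats that CR line.

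**Sum built on longest diameter.** Protocol 9.2 states: "A sum of the longest diameter (LD) for *all target lesions* will be calculated and reported as the baseline sum LD". In Protocol 9.3, PR is "At least a 30% decrease in the sum of the LD of target" lesions from baseline. PD is "At least a 20% increase in the sum of the LD of target" lesions from the smallest recorded sum, plus an absolute rise of at least 5 mm. SD is whatever lies between. SAP Appendix 1.1 carries the same definitions. Neither document makes an exception for nodes.

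**A separate sentence.** Section 9 also says: "Lesions will only be considered measurable when they are superficial (e.g., skin nodules and palpable lymph nodes"). The same section sets a spiral-CT size threshold for measurable lesions, and 9.1 names CT and MRI as the best methods for measuring target lesions.

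**The concern.** A target node is admitted on one dimension, cleared on that same dimension, and scored between those points on another. When the two dimensions change by different amounts, the text supports two categories for one scan.

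DCR counts CR, PR and SD as success, so the SD/PD line decides the primary endpoint. ORR and PFS use the same categories. Under SAP Appendix 1.2, one SD assessment at about 8 weeks is enough for a best response of SD, so a single reading can settle a patient's result. Imaging follows institutional practice (Protocol 5.4 and 9.1) and neither document describes a central reading. Sites that measure nodes differently would therefore not be brought into line later.

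The superficial-only sentence raises a different issue. Inclusion criterion 6 refers to Section 9 for measurable disease, so the sentence bears on who is eligible.

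**Working it through.** The plan gives no figure on this point to reproduce. The check applies the plan's own thresholds to node sizes that are **assumed**, since the documents give none.

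**Thresholds (Protocol 9 and 9.3; the response criteria also in SAP Appendix 1.1)**
- PD: at least +20% and at least +5 mm over the smallest sum.
- PR: at least 30% below the baseline sum.
- Node measurable: short axis at least 15 mm. Nodal CR limit: short axis below 10 mm.

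**Formula.** Change = (follow-up sum − reference sum) / reference sum. Each case has one follow-up scan, so baseline is also the smallest earlier sum.

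| Case (short x long axis, mm) | Longest diameter, as written | Short axis for nodes |
|---|---|---|
| A. 15 x 30 to 20 x 35 | 5/30 = +16.7%: SD | 5/15 = +33.3%, +5 mm: PD |
| B. 15 x 30 to 18 x 36 | 6/30 = +20%, +6 mm: PD | 3/15 = +20% but only +3 mm: SD |
| C. Node 15 x 30 to 22 x 34, plus a stable 20 mm non-nodal lesion | 50 to 54: 4/50 = +8%: SD | 35 to 42: 7/35 = +20%, +7 mm: PD |
| D. 16 x 25 to 16 x 31 | 6/25 = +24%, +6 mm: PD | 0%: SD |
| E. 15 x 30 to 9 x 25 | −5/30 = −16.7%: short of PR | −6/15 = −40%; 9 mm is below the CR limit |
| F. 20 x 30 to 13 x 28 | −2/30 = −6.7%: SD | −7/20 = −35%: PR |

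**Direction.** In A and C the longest diameter gives SD where the short axis gives PD. In B and D it is the reverse. Case B is not isolated. If a 15 x 30 mm node grows in proportion by a fraction g, the longest diameter gives PD from g = 20% (30 x 0.20 = 6 mm, above 5 mm). The short axis needs 15 x g of at least 5 mm, so g of at least 33.3%. Between 20% and just under 33.3%, the written rule gives PD and a short-axis rule gives SD.

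**Shrinkage.** Case E meets the nodal CR limit while the sum has not reached PR, so the same table supports CR or SD. Case F is SD or PR depending on the axis. These cases bear on ORR. They do not change DCR at a scan late enough for SD to count under SAP Appendix 1.2, because CR, PR and SD all count as control.

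**Weight of one patient in DCR.** 1/24 = 4.2 percentage points and 1/18 = 5.6 at the planned arm totals; 1/50 = 2.0 at the expanded size. How many patients would be affected cannot be derived.

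**Superficial-only sentence, set against its neighbours.** It conflicts with the spiral-CT threshold in Section 9, with CT and MRI as preferred methods in 9.1, with 9.2 (target lesions may be followed by imaging or clinically) and with baseline CT or MRI in 5.2. Inclusion criterion 10 also expects patients with liver metastases. Read literally, a patient with only deep lesions would fail inclusion criterion 6.

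**The case against.** **A reader might infer that the longest-diameter rule inflates DCR and PFS.** The documents do not support a direction. Cases B and D show the rule calling PD where the short axis would not, and in such cases moving to the short axis would raise DCR.

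**A reader might say that nodal progression is being missed.** That is partly circular. The documents define PD by the longest-diameter sum, and nowhere do they say that the nodal short axis belongs in it. What they show is an inconsistent choice of axis. This stands, and it limits the finding to inconsistency.

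**A reader might take case E as a response plainly misread as SD.** It is ambiguous between CR and SD, because target-lesion CR is not defined by the sum.

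**A reader might conclude that patients with only liver or lung lesions are excluded.** The surrounding text makes that implausible. The sentence looks like a drafting omission and has no role in the nodal SD/PD problem.

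Other points reduce the weight. Up to five target lesions are allowed, so one node may be diluted. New lesions trigger PD whatever the sum. The analysis is descriptive, and SAP 4.1 states that no hypothesis is tested. Sites may follow the cited RECIST 1.1 rather than the protocol's wording. That last point does not remove the problem: Section 9 instructs use of the criteria it sets out, and if some sites follow the citation and others the text, identical scans may be scored differently.

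**Conclusion.** The inconsistency is real and can be shown from the documents alone. Nodal eligibility and CR use the short axis; PR, SD and PD use a longest-diameter sum that includes nodes. The resulting category can differ in either direction at the SD/PD boundary of the primary endpoint, and shrinkage cases can affect ORR.

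The net effect on DCR and PFS is unknown in sign and size. The worked cases rest on assumed node dimensions, and the share of patients with nodal target lesions is not given. The conclusion is that the text should be repaired and the axis actually used should be reported, not that DCR is biased upward.

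The superficial-only sentence is a separate contradiction, affecting the definition of measurable disease and, through inclusion criterion 6, eligibility.

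**What to change.** 1. In Protocol 9.2 and 9.3 and SAP Appendix 1.1, define one sum of diameters: longest diameter for non-nodal target lesions, short axis for nodal target lesions. Derive PR, SD and PD from it. This matches the axis the protocol already uses for nodal eligibility and CR.
2. Write nodal CR as a reduction in short axis *to* below 10 mm. The present wording can be read as an amount of shrinkage, whereas the non-target row states a size.
3. If scans have already been read, do not silently redefine the endpoint. Report which axis was used for nodal targets, and re-derive the nodal cases with the other axis as a sensitivity analysis for DCR, ORR and PFS.
4. Limit the superficial-only sentence in Protocol Section 9 to lesions measured by clinical examination, so that lesions measured by CT or MRI remain measurable.

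**Cost.** Wording changes in two documents. The main downside is re-entry of nodal short axes from existing scans. The short axis is already needed at baseline and to call CR, but it may not have been recorded at every follow-up. The SAP's latest listed amendment is dated September 2020 and SAP 4.2.2 describes study conduct in the past tense, so the sensitivity analysis may be the practical part of this fix.

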### 9.3 Response Criteria

	Evaluation of target lesions
Complete Response (CR):	Disappearance of all target lesions
	Any pathological lymph nodes must have reduction in short
	axis of <10mm
Partial Response (PR):	At least a 30% decrease in the sum of the LD of target
	lesions, taking as reference the baseline sum LD
Progressive Disease (PD):	At least a 20% increase in the sum of the LD of target
	lesions, taking as reference the smallest sum LD recorded
	since the treatment started. In addition to the increase of
	20%, the sum must also demonstrate an absolute increase of
	at least 5mm. The appearance of one or more new lesions is
	also considered progression
Stable Disease (SD):	Neither sufficient shrinkage to qualify for PR nor sufficient
	increase to qualify for PD, taking as reference the smallest
	sum LD since the treatment started
	Evaluation of non-target lesions
Complete Response (CR):	Disappearance of all non-target lesions and normalization of

	Evaluation of non-target lesions
Complete Response (CR):	Disappearance of all non-target lesions and normalization of
	tumor marker level. All lymph nodes must be non-
	pathological in size (<10mm short axis)
Stable Disease (SD):	Persistence of one or more non-target lesion(s) and/or
	maintenance of tumor marker level above normal limits
Progressive Disease (PD):	Appearance of one or more new lesions and/or unequivocal
	progression of existing non-target lesions

### 9.4 Evaluation of Best Overall Response

The best overall response is the best response recorded from the start of the treatment until disease progression/recurrence and is determined as indicated in the table below:

Target	Non-Target lesions	Evaluation of	Overall response
lesions		New lesions	
CR	CR	No	CR
CR	Non-CR/non-PD	No	PR
CR	not evaluated	No	PR
PR	Non-PD or not all evaluated	No	PR
SD	Non-PD or not all evaluated	No	SD
PD	Any	Yes or No	PD
Any	PD	Yes or No	PD
Any	Any	Yes	PD

### 10 PLANNED STATISTICAL METHODS

### 10.1 General Considerations

Because of the nature of this study, no formal statistical analysis is planned. Evaluation of the data will consist primarily of summary displays (i.e., descriptive statistics and graphs).

### 10.2 Determination of Sample Size

The following number of colorectal cancer patients will be enrolled based on a two-stage Simon design with an alpha of 5% and a power of 80% to detect a disease control rate improvement for Cetuximab and Panitumumab from about 30% (historical DCR for 3rd and 4th line colorectal cancer) to 60%, and a disease control rate improvement for Capecitabine from about 15% (historical DCR for 3rd line colorectal cancer) to 60%

Disease	Control	Rate -	- Third	Line
---------	---------	--------	---------	------

	Monotherapy (Historical)	Combination * (Historical)	Combination with BBI608 (Expected)
Cetuximab	30-40% 	~ 63% 10-15	60% or more
Panitumumab	30-40% 	~ 68% 	60% or more
Capecitabine	~ 15% 	~ 45% 	60% or more

\* Cetuximab + Irinotecan
Panitumumab + Irinotecan
Capecitabine + Mitomycin C

### Simon two-stage design for Phase II

	Patient number									
Combo Therapy	Stage 1	Stage 2	Total*							
Cetuximab	8	16	24							
Panitumumab	8	16	24							
Capecitabine	6	12	18							

\*If any of the three arms reach a DCR of 60% or more at the end of Simon Stage 2, a one-time option to expand accrual to a total sample size of up to 50 patients may be implemented for each arm.

For the Cetuximab and Panitumumab combination cohorts, if the disease control rate in stage 1 reaches 3 of 8 or above, additional patients will be enrolled into the stage 2 cohort. For the Capecitabine combination cohort, if the disease control rate in stage 1 reaches 2 of 6 or above, additional patients will be enrolled into the stage 2 cohort.

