#### **Statistical Methods:**

In general, categorical variables will be summarized as the number and percentage of patients in each category. Continuous variables will be summarized by the mean, standard deviation, median, minimum, and maximum.

The primary population for the efficacy evaluation will be the evaluable population, defined as patients who have been treated with at least 80% of 1 complete cycle of BBI608 and a combination drug. The primary endpoint will be disease control rate, defined as the proportion of patients with a documented complete response, partial response and stable disease (CR + PR + SD) based on RECIST. The secondary endpoints will include progression-free survival (PFS) and overall survival (OS). PFS will be calculated from the date of patient enrolment into the trial until documented disease progression based on RECIST. OS will be calculated from the date of patient enrolment into the trial until death.

Patient sample size for each combination regimen is calculated based on a power of 80 and a one-sided alpha of 5% to detect a disease control rate improvement for Cetuximab and Panitumumab from about 30% (historical DCR for 3rd and 4th line colorectal cancer) to 60% and for Capecitabine from about 15% (historical DCR for 3rd line colorectal cancer) to 60%.

Safety analyses will include adverse events, SAEs, laboratory tests, and physical examination changes from baseline. The safety population will include all patients who have received any amount of BBI608 and the combination drug. All patients receiving at least one daily dose of BBI608 will be considered evaluable for safety analyses. In addition to the evaluation and categorization of adverse events, listings of laboratory test results collected at baseline and during the study will be generated. Descriptive statistics summarizing the changes in those laboratory tests over time will be presented.

Analysis and Sample size for sub-cohorts:

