4. HYPOTHESES AND DECISION RULES

4.1. Statistical Hypotheses

There is no hypothesis testing in this study.

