4.2.2. Simon's Design Decision Rule

The Simon's design decision rule is described in Section 4.1 of protocol amendment 2 [5], but the study was not conducted following the Simon two-stage design and no Simon's design decision rule was applied.

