4.3. Sample Size Justification

The sample size for this study was determined by clinical rather than statistical considerations. The exact number of patients estimated for this trial is dependent on the number of patient cohorts investigated based on the toxicity encountered. It is expected that up to a total of approximately 50 response evaluable patients will be enrolled in each combination arm during the study. Patients who have received at least one cycle of study treatment unless discontinued due to death or PD and have had at least one disease assessment following the initiation of therapy will be considered evaluable for response.

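### Do the 3-of-8 gate and the missing final count make the stated 5% alpha and 80% power wrong for the cetuximab and panitumumab arms?

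*Protocol*

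**What the plan says.** Protocol sections 4.1 and 10.2 take the patient numbers from a "two-stage Simon design with an alpha of 5% and a power of 80" per cent. The design is to detect a rise in disease control rate (DCR) from about 30% to 60% for cetuximab and panitumumab, and the synopsis adds that alpha is one-sided. The table gives 8 patients in stage 1 and 16 in stage 2, 24 in all, for each of these arms. Enrolment goes on to stage 2 "if the disease control rate in stage 1 reaches 3 of 8 or above".

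Neither document gives a count out of 24 that would be declared a success. The only threshold after stage 2 is in the table footnote: arms that "reach a DCR of 60% or more at the end of Simon Stage 2, a one-time option to expand accrual", to at most 50 patients.

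Protocol 10.1 plans descriptive summaries and no formal analysis. SAP 4.1 states: "There is no hypothesis testing in this study". SAP 4.2.2 records that "the study was not conducted following the Simon two-stage design" and that its decision rule was not used. SAP 4.3 adds: "The sample size for this study was determined by clinical rather than statistical considerations". SAP 5 plans no formal interim analysis. SAP 8.2.2 reports DCR with an exact two-sided 95% confidence interval in the response evaluable set, and repeats the estimate in the safety set as a sensitivity analysis.

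**The concern.** Alpha and power belong to a complete rule: both stage sizes, the stage 1 boundary and the final boundary. The protocol gives three of the four and still claims 5% and 80%. The sizes 8 and 24 are also those of the Simon optimal design for 30% against 60%, which stops at 3 or fewer of 8. The protocol continues at 3, so its gate equals that design's stopping number, and an off-by-one slip comes to mind.

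If the rule were in use, the gate would matter. At a true DCR of 30%, an arm would continue with probability 44.8% instead of 19.4%. A reader might also attach 5% and 80% to the reported DCR, although the SAP gives a different basis for the sample size.

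**Working it through.** **Inputs.** p0 = 0.30, p1 = 0.60, n1 = 8, n2 = 16, N = 24, alpha at most 5%, power at least 80% (protocol 10.2); one-sided (synopsis); continue at c = 3 of 8 (protocol 4.1 and 10.2). The final count r is not stated.

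**Formula.** With futility stopping only, the probability of declaring success at true rate p is

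S(p) = Σ from x = c to 8 of Bin(x; 8, p) × P[Bin(16, p) ≥ r − x].

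Alpha is S(0.30) and power is S(0.60).

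**Reproducing 8 + 16 = 24.** A search over two-stage designs for the smallest expected size under p0 returns n1 = 8, N = 24, continue at 4, success at 11, with alpha 4.6% and power 80.6%. The minimax design for the same inputs is n1 = 10, N = 17. The sizes therefore match the optimal design, a term the protocol does not use.

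**Stage 1 with each gate.**
- True rate 0.30: P(X ≤ 2 of 8) = 0.0576 + 0.1977 + 0.2965 = 0.5518, so the chance of continuing at 3 is 0.4482. P(X = 3) = 0.2541, so the chance of continuing at 4 is 0.4482 − 0.2541 = 0.1941.
- Expected size at 0.30: 8 + 16 × 0.4482 = 15.2 for gate 3; 8 + 16 × 0.1941 = 11.1 for gate 4.
- True rate 0.60: wrongful early stopping is 5.0% for gate 3 and 17.4% for gate 4.

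The lower gate lets more inactive arms through and loses fewer active ones. That is a trade-off and does not by itself break the design.

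**Complete rules.**

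| Continue at | Success at | Alpha | Power | Meets 5% and 80%? |
|---|---|---|---|---|
| 3 of 8 | 11 of 24 | 6.5% | 91.3% | No (alpha) |
| 3 of 8 | 12 of 24 | 2.9% | 86.1% | Yes |
| 3 of 8 | 13 of 24 | 1.1% | 77.2% | No (power) |
| 4 of 8 | 11 of 24 | 4.6% | 80.6% | Yes |

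Alpha and power both fall as the count rises. With the written gate, alpha therefore requires at least 12 and power at most 12. The stated inputs leave one possible count.

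**Was 4 of 8 intended?** The capecitabine row of the same table tests this. For 15% against 60% the optimal design is n1 = 3, N = 6, continuing at 1 of 3 and succeeding at 3 of 6. Subtracting the path with 0 of 3 and then 3 of 3:
- Alpha = P[Bin(6, 0.15) ≥ 3] − 0.85³ × 0.15³ = 0.0473 − 0.0021 = 0.045.
- Power = P[Bin(6, 0.60) ≥ 3] − 0.40³ × 0.60³ = 0.8208 − 0.0138 = 0.807.

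The protocol has 6 + 12 = 18 there. The table does not follow the optimal criterion throughout, so a 4-of-8, 11-of-24 rule is conjecture.

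**Is the 60% footnote the missing rule?** 0.60 × 24 = 14.4, hence 15 of 24, with alpha 0.1% and power 48.6%. For capecitabine 0.60 × 18 = 10.8, hence 11 of 18, with power 56.0%. Neither reaches 80%, and the footnote speaks only of expanding accrual.

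**The case for a change.** The case for a change is that DCR is the primary endpoint, and a protocol claiming 5% and 80% should let a reader see what result would have met the claim. The match with the optimal design is exact in both sizes, and the written gate is that design's stopping number, so a slip is plausible. The documents also differ on where the sample size came from: protocol 10.2 says a Simon design, SAP 4.3 says clinical considerations, and SAP 2.1 still describes enrolment as based on Simon. Correcting this would need only wording.

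Parts of this stand. The final count is missing, the origin of the 3-of-8 gate cannot be settled from the documents, and the two accounts of the sample size do differ. SAP 4.2.2 largely explains that last point: the protocol describes what was planned, and the SAP says it was not carried out.

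The inference that something must be repaired does not stand. A success count written into the protocol now would be retrospective, could be mistaken for a prespecified one, and would sit beside the SAP's expectation of up to about 50 response-evaluable patients per arm. It would also cost more than wording, because protocol 13.1 requires ethics approval before a modification is implemented. A SAP or report sentence separating 5% and 80% from the trial as run would do no harm, but it would mostly repeat SAP 4.1 and 4.2.2.

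**Conclusion.** The design statement is incomplete, but no figure in it is shown to be wrong. The written gate with 24 patients meets both limits at 12 of 24 (alpha 2.9%, power 86.1%), and no other count does. The effect on the analysis is nil: nothing is tested against 30%, no Simon rule was applied, and the DCR estimate with its exact interval uses neither the gate nor a final count.

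This rests on two assumptions. The binomial calculation takes the protocol's inputs as exact, although it gives the 30% as approximate. The SAP's account of how the study was run is taken at face value. If a report were to claim activity at 5% alpha, the missing count would matter, but the SAP plans no such claim. No change to the plan is needed.
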